11.0 TOXICITIES/SIDE EFFECTS

Toxicity will be described according to NCI Common Toxicity Criteria (Version 3.0)

11.1 Doxil®

- f* Cardiac toxicity: cardiomyopathy and/or congestive heart failure. Possibly non-specific arrhythmias
- f* Myelosuppression. Leukopenia more common than thrombocytopenia and anemia
- f* Infusion reactions: shortness of breath, facial swelling, headache, chills, chest pain, back pain, tightness in the chest and throat, fever, tachycardia, pruritus, rash, cyanosis, syncope, bronchospasm, asthma, apnea and/or hypotension, anaphylaxis
- f* Palmar-plantar erythrodysesthesia (hand-foot syndrome)
- f* Stomatitis
- f* Pregnancy, Category D risk
- f* Injection site reactions. An irritant, not a vesicant.
- f* Asthenia
- f* Nausea/vomiting

11.2 Targretin®

**Memorial Sloan-Kettering Cancer Center
IRB Protocol**

IRB#: 05-098 A(6)

- f* Hyperlipidemia: hypertriglyceridemia more common than hypercholesterolemia
- f* Hypothyroidism
- f* Headache
- f* Fever
- f* Asthenia, myalgia, arthralgia
- f* Rash
- f* Pancreatitis (associated with hypertriglyceridemia)
- f* Reversible liver function abnormalities
- f* Leukopenia/neutropenia
- f* Anemia
- f* Pregnancy, Category X risk

11.2.1 Serious Adverse Event (SAE) Reporting

For Participating Sites:

Any SAE will be reported to the local institution's IRB. In addition, it will need to be sent to MSKCC as the coordinating center and Ortho Biotech as soon as possible but no later than 5 days from the onset of the event.

Ortho Biotech will be notified of SAEs within 24 hours by faxing a completed MedWatch 3500 form to [contact]; this form must also be faxed to the MSKCC principal investigator, [name] ([contact]; [contact]; email: [contact]). The sites should fax to Ortho Biotech and MSKCC at the same time.

The Study PI will fax a copy of all SAE's within 5 days to outside site principal investigators to report to their own local IRB's.

Participating sites should send the following information to the coordinating center:

1. The initials of the subjects, patient MRN #, MSKCC protocol# and title
2. The date the event occurred
3. A description of the SAE
4. An explanation of how the SAE was handled
5. A description of the subject's condition
6. Indication if the subject remains on the study
7. Indication if the event is considered related to the treatment (drug, device, intervention)
8. Indication if an amendment will need to be made to the protocol and/or consent form as a result of the SAE.

12.0 CRITERIA FOR THERAPEUTIC RESPONSE/OUTCOME ASSESSMENT

- 12.1 At 16 weeks (completion of Doxil® treatment) and after 16 weeks of Targretin® treatment: CT scans of chest, abdomen and pelvis for TNM stage IV patients who had positive findings prior to treatment.

**Memorial Sloan-Kettering Cancer Center
IRB Protocol**

IRB#: 05-098 A(6)

- 12.2 History and physical examination including skin assessment
- 12.3 Karnofsky performance status.
- 12.4 CBC with Sézary cell count and/or flow cytometry in patients with Sézary syndrome.
- 12.5 Assessment of response status and any residual toxicity will be performed 4 weeks after completion of treatment.
- 12.6 Biopsy of residual lesions 4 weeks after the completion of treatment if clinical complete remission is suspected.
- 12.7 Dermatologic evaluation of response

Dermatologic responses will be determined by the Severity-Weighted Assessment Tool (SWAT), a standardized approach to measuring the extent and severity of overall skin disease in patients with CTCL. It will be briefly described and full details are provided in an appendix. The purpose of this description is to optimize intra-observer objectivity and to minimize the potential for intra-observer and inter-observer variability in the measurement of overall skin disease. Only physicians who received training will be permitted to conduct SWAT assessments during the clinical study. It is essential that physicians adhere as closely as possible to the prescribed procedures so as to reduce measurement error and variability. All efficacy assessments should be performed by the same physician for each patient whenever possible. Physicians will be instructed not to examine previous SWAT assessments and full body photographs prior to conducting the current SWAT assessment.

1. Total Body Surface Area (TBSA) Involvement by Skin Disease

The body is divided into 12 regions with pre-assigned %TBSA based on the burn literature. The extent of skin disease in each region is quantified by using the patient's palm to measure the %TBSA involvement within region:
Patient's palm with 4 fingers (excluding the thumb) is 1% of TBSA
Patient's palm without fingers is 0.5% of TBSA.

The patient's palm with 4 fingers is traced on a transparency sheet at the baseline visit, using a permanent marker that will not rub off or smear. The transparency of the patient's palm should be used in all SWAT assessments during the course of the clinical study. The transparency will be labeled with the patient's study ID number kept in the patient's study file on site. Using the baseline visit transparency of the patient's palm, the investigator will measure and record on the case report form (Example of table from CRF is given below) the %TBSA for each lesion type within each of the 12 regions.

2. Severity Weighting Factor

The severity weighting factors will be the following:

**Memorial Sloan-Kettering Cancer Center
IRB Protocol**

IRB#: 05-098 A(6)

1= patch (flat erythema or erythema with mild infiltration)
2=plaque (e levated erythema or erythema with moderate infiltration)

4= tumor or ulceration (erythema with fissuring, ulceration or tumor)

Patch is defined as abnormal skin not elevated from normal skin. A plaque is defined as abnormal skin elevated from normal skin by < 5 mm. A plaque elevated ≥5 mm is a tumor.

3. Calculating Skin Scores

The sum of %TBSA by lesion is derived by summing the %TBSA from all regions affected by the lesion. The sum of %TBSA across lesion types (patches, plaques and tumors) within each region can not exceed the %TBSA for the region. For example, the %TBSA for the head region is 7%. The sum of %TBSA across lesion types from head can only range from 0-7%. The skin score subtotal by lesion type are derived by multiplying the sum of %TBSA for patches from all regions by 1, sum of %TBSA of plaques from all regions by 2, and the sum of %TBSA of tumors or ulcers from all regions by 4. The skin score total is derived from summing the skin score subtotals for patches, plaques and tumors or ulcers. The skin score total is dimensionless with a scale of 0 to 400.

Region	% TBSA for the region	% TBSA Patch (or flat erythema)	% TBSA Plaque (or elevated/indurated erythema)	% TBSA Tumor/ Ulceration (or erythema w/fissuring, ulceration)
Head	7			
Neck	2			
Anterior Trunk	13			
Posterior Trunk	13			
Buttocks	5			
Genitalia	1			
Upper Arms	8			
Forearms	6			
Hands	5			
Thighs	19			
Lower Leg	14			
Feet	7			
% BSA by category	100			
Severity Weighting Factor		X 1	X 2	X 4
Skin Score Subtotal				

**Memorial Sloan-Kettering Cancer Center
IRB Protocol**

IRB#: 05-098 A(6)

Responses will be determined by the criteria described in the table below. Progression of disease while on treatment should be confirmed by a second assessment 1-4 weeks later so that patients who experience a temporary flare of disease due to skin infection or other intercurrent illnesses are not removed from the study prematurely.

Assessment	Description	Status
Completely clear	No evidence of disease; 100% improvement	CCR
Marked Improvement	Greater than or equal to 50% decrease in skin scores compared to baseline and improvement is maintained for 4 weeks	PR
Slight Improvement	Less than 50% decrease in skin scores compared to baseline	SD
Worse	$\geq 25\%$ increase in skin scores compared to baseline while the patient is actively taking the study drug or $\geq 50\%$ increase in the sum of the products of the greatest diameters of pathologically positive lymph nodes (should be documented by biopsy) compared to baseline while the patient is actively taking the study drug.	PD

Assessment of Overall Skin Disease

Pruritus Relief (Appendix 1)

The intensity of pruritus will be evaluated by the patient at baseline, at the week 16 (end of treatment with Doxil®) and week 32 (after 16 weeks of treatment with Targretin®) using a 1-10 point scale, where 0 is no pruritus and 10 is the worst imaginable pruritus. A 3-point decrease in pruritus intensity confirmed by a second assessment at least 4 weeks later without an increase in the use of anti-pruritic medications is considered clinically significant in those whose pruritus score is ≥ 3 on the 0-10 point scale at baseline.

4. As a secondary goal, index lesion severity will be evaluated by a modified Composite Assessment Scale (Appendix 2). These are measurements of skin disease that have been employed and validated in the phase II-III studies of Targretin® and in the current MSKCC trial of Targretin® of Intron-A® (IRB #01-128) in CTCL. Up to 4 index skin lesions will be chosen from representative patch, plaque and tumor lesions, and erythrodermic lesions. For erythrodermic patients, a 10x10 cm. area, easily identified by anatomic landmarks will be chosen and assessed by the same scale. These index lesions will be photographed and assessed at the same time as the SWAT assessment.

In the Phase II-III studies of Targretin capsules in CTCL, the Composite Assessment (CA) of Index Lesion Disease Severity was based on a core element of the summation of index lesion

**Memorial Sloan-Kettering Cancer Center
IRB Protocol**

IRB#: 05-098 A(6)

clinical signs . Up to a maximum of five (5) cutaneous T-cell lymphoma lesions were designated as index lesions. If the patient had five or fewer CTCL lesions, then all CTCL lesions were designated as index lesions. If the patients had more than five CTCL lesions, then five lesions that were representative of the patient's overall cutaneous disease were designated as index lesions. The index lesions were preferably separate and distinct from other lesions in order to minimize the chance of lesion confluence. Individual index lesion clinical signs and symptoms were to have been graded at each visit according to a 0-to-8 point scale (see Table). A CA summation was generated by summing the grades for each index lesion for each clinical sign. To determine the area of each index lesion, the longest diameter and the longest diameter perpendicular to this diameter of each index lesion were to have been measured to the nearest millimeter. The area in square centimeters was then converted to a 0-to-18 scale in order to provide a means for integrating the area into the CA summation of grades (see Table). The summation of CA grades at baseline was divided into the summation of CA grades at each subsequent post-baseline study visit to determine the CA ratio to provide an objective measure of the patient's response to treatment (e.g., a CA ratio <1.0 indicated improvement in disease and a ratio >1.0 indicated a worsening of disease). This CA score was found to correlate with the Physicians Global Assessment, which is replaced by SWAT in this study.

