1.0 PROTOCOL SUMMARY AND/OR SCHEMA

Cutaneous T-cell lymphoma: TNM stages IB, IIA, IIB-IV, either newly diagnosed or previously treated with active measurable disease

Sample Size: 37 patients

Multi-Center Study : Participating sites include M.D. Anderson Cancer Center, Yale University School of Medicine, New York University Medical Center, Hackensack University Medical Center

IND Status: Non-IND

Criteria to be used for response evaluation:

The evaluation of cutaneous tumor burden in CTCL is an evolving process. Skin tumor and lymph node assessments will be performed prior to treatment and after eight cycles of Doxil® according the Severity-Weighted Assessment Tool (SWAT) for CTCL response that is currently employed in IRB 02-078 and 04-051. Also the completion of treatment, history and general physical examination, Karnofsky performance status, CBC with Sézary cell count for patients with Sézary syndrome, and CT scans of the chest, abdomen and pelvis for patients with TNM stage IV CTCL will be obtained. These studies will also be obtained prior to treatment. If clinical complete remission of target skin lesions is suspected, skin biopsies will be repeated following completion of treatment.

Dosing/Regimen:

1. Doxil®Dose: 20mg/m² intravenously. Frequency: 2 weeks. Number of Cycles: 8
2. Targretin®Dose: 300mg/m² orally Frequency: Daily for at least 16 weeks

Schema:

Doxil® every 2 weeks x 8→response assessment→Targretin® x 16 weeks→response assessment, CR/PR→continue Targretin® until relapse.

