The two clinical studies enrolled a total of 152 patients, 102 of whom had disease refractory to at least one prior systemic therapy, 90 with advanced disease and 12 with early disease. This is the patient population for whom Targretin® capsules are indicated. Patients were initially treated with a starting dose of 650 mg/m²/day with a subsequent reduction of starting dose to 500 mg/m²/day. Neither of these starting doses were tolerated, and the starting dose was then reduced to 300 mg/m²/day. If, however, a patient on 300 mg/m²/day of Targretin® capsules showed no response after eight or more weeks of therapy, the dose could be increased to 400 mg/m²/day. Tumor response was assessed in both studies by observation of up to five baseline defined index lesions using a Composite Assessment of Index Lesion Disease Severity (CA). This endpoint was based on a summation of the grades, for all indexes lesions, of erythema, scaling, plaque elevation, hypopigmentation or hyperpigmentation, and area of involvement. Also considered in response assessment was the presence or absence of cutaneous tumors and extracutaneous disease manifestations.

All tumor responses required confirmation over at least two assessments separated by at least four weeks. A partial response was defined as an improvement of at least 50% in the index lesions without worsening, or development of new cutaneous tumors or non-cutaneous manifestations. A complete clinical response required complete disappearance of all manifestations of disease, but did not require confirmation by biopsy.

At the initial dose of 300 mg/m²/day, 1/62 (1.6%) of patients had a complete clinical tumor response and 19/62 (30%) of patients had a partial tumor response. The rate of relapse (25% increase in CA or worsening of other aspects of disease) in the 20 patients who had a tumor response was 6/20 (30%) over a median duration of observation of 21 weeks, and the median duration of tumor response had not been reached. Responses were seen as early as 4 weeks and new responses continued to be seen at later visits.

**Memorial Sloan-Kettering Cancer Center
IRB Protocol**

IRB#: 05-098 A(6)

Targretin® capsules are supplied as 75-mg off-white, oblong soft gelatin capsules, imprinted with “Targretin,” in high density polyethylene bottles with child-resistant closures.

Bottles of 100 capsules..... NDC 64365-502-01

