10.0 EVALUATION DURING TREATMENT/INTERVENTION

10.1 Treatment visits every 2 weeks for Doxil® administration for 16 weeks. At each visit: history, physical exam, KPS, toxicity assessment, CBC, platelet count.

10.2 Tumor assessment within 2 weeks following the last dose of Doxil®, optimally between 7 and 14 days. For patients with stage IV disease (TNM) with baseline lymphadenopathy on CT scans of chest, abdomen and pelvis: repeat CT scans of chest, abdomen and pelvis. Patients with Sezary syndrome will have Sézary cell count and/or flow cytometry. Patients who have a CCR should have a biopsy to document a pathological CR. Two item self-reported pruritus questionnaire will be administered at time of tumor assessment. The details for tumor assessments at 16 and 32 weeks are described in Section 12.0 and in the Table in Appendix 3.

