Appendix 3: Schedule of Protocol Events																
Week	PreRx	W .2	W .4	W .6	W .8	W .10	W .12	W .14	W .14-16	W .14-16	W .16-18	W .18-20	W .22-24	W .26-28	W .30-32	
	Rx Dose 1	Dose 2	Dose 3	Dose 4	Dose 5	Dose 6	Dose 7	Dose 8		Rx Day 1	Rx W .2	Rx W .4	Rx W .8	Rx W .12	Rx W .16	
Resp. Eval.									X						X	
Rx	Do xil	Do xil	Do xil	Do xil	Do xil	Do xil	Do xil	Do xil		Targ retin	Targ retin	Targ retin	Targ retin	Targ retin	Targ retin	
Hx/Px	X	X	X	X	X	X	X	X	X	X	X	X	X	X	X	
KPS	X	X	X	X	X	X	X	X	X	X	X	X	X	X	X	
Toxicity assess.		X	X	X	X	X	X	X	X	X	X	X	X	X	X	
Tumor measurements	X								X***						X***	
Skin score																
Pruritus questionnaire	X								X						X	
CBC	X	X	X	X	X	X	X	X	X	X	X	X	X	X	X	
Fasting: Trigl.*** Cholest.	X								X		X	X	X	X	X	
Lytes, BUN, Cr., AST, ALT, alk. phos., bili., TP, alb., Ca, amylase, UA, gluc	X								X		X	X	X	X	X	
Urinal.	X															
T4, TSH	X								X		X	X	X	X	X	
Echo/MUGA	X															
CT c/a/p*	X								X						X	
Sézary cell CT/Flow	**** X								X						X	
beta-HCG**	X								X							
*Pts. with stage IV (TNM)																
**premenopausal women within 7 days																
***biopsy of residual lesions if CCR																
****fasting triglyc. obtained at each MD visit																
*****Pts. with Sézary syndrome																

Schedule of Protocol Events

**Memorial Sloan-Kettering Cancer Center
IRB Protocol**

IRB#: 05-098 A(6)

Appendix 4

DATA COLLECTION FORM SCHEDULE

FORM	BASELINE	CYCLE	OFFSTUDY	WHEN APPLICABLE
Demographic, Disease & Prior Treatment Form	X			
Comorbidity Form	X			
Original Pathology Reports*	X			
Original Radiology Reports	X			
Treatment & Treatment Modification Form		X	X	
Physical Exam Form		X	X	
Laboratory Form	X			
Toxicity Form		X	X	
Concomitant Drug Form	X	X	X	
Hospitalization Form				X
Patient Status & Outcome Form				X

* Pathology report must be faxed to the MSKCC Clinical Trials Office [contact] at the same time as patient registration that confirms patient has Cutaneous T-Cell Lymphoma.

Schedule:

Baseline: Forms to be submitted within two weeks of registration.

Cycle: To be completed after each cycle and submitted every 4 weeks.

Off-study: To be submitted within four weeks of the protocol completion.

Please submit forms to:

**[name], Research Study Assistant
Memorial Sloan-Kettering Cancer Center
[name]
[name]
[contact]**

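### Partial response must last 4 weeks but complete clearance has no duration, endpoint CR is not defined, and the confirming biopsy has conflicting times, so the secondary CR rate can be biased upward

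*Combined protocol and SAP*

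**What the plan says.** Section 12.7 states that its table determines response. The rows that matter here are:

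- **CCR:** "No evidence of disease; 100% improvement". No maintenance period and no biopsy criterion.
- **PR:** "Greater than or equal to 50% decrease in skin scores compared to baseline and improvement is maintained for 4 weeks".
- **SD:** a decrease of less than 50%.

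Section 12.7 also asks for a second assessment before progression on treatment is accepted (1-4 weeks later) and before pruritus relief counts as clinically significant (at least 4 weeks later).

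Section 2.0 makes CR + PR the secondary objective, and Section 14.0 lists the complete and partial response rates as secondary endpoints. Neither defines CR.

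The biopsy after a suspected complete response appears in four places:

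- Section 10.2, on the assessment after Doxil: "Patients who have a CCR should have a biopsy to document a pathological CR".
- Appendix 3, as a footnote to the tumor measurements in the week 14-16 and week 30-32 columns: "biopsy of residual lesions if CCR".
- Section 12.6: "Biopsy of residual lesions 4 weeks after the completion of treatment if clinical complete remission is suspected".
- Section 1.0: "skin biopsies will be repeated following completion of treatment".

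Section 12.5 adds: "Assessment of response status and any residual toxicity will be performed 4 weeks after completion of treatment". Sections 4.2 and 10.6 allow responders to stay on Targretin until relapse or progression.

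**The concern.** The most favorable category in the table has the weakest evidence requirement. PR, progression and pruritus relief each need a later confirmation; CCR does not. Section 5.0 reports that the earlier Targretin studies held every response to one standard: "All tumor responses required confirmation over at least two assessments separated by at least four weeks". The protocol gives no reason for exempting complete clearance.

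The second gap makes the first one matter. The table has no complete-response row other than CCR, and the endpoint sections say only CR. One site or analyst could count every CCR and another only the biopsy-documented ones. The biopsy itself has more than one stated time, and *completion of treatment* is not defined for a patient whose Targretin is open-ended.

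At stake is the CR rate, a named secondary endpoint of a single-arm, multi-center trial. With no concurrent control, its meaning depends on a definition that can be set beside historical rates.

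**Working it through.** **1. The plan's own figures.** The documents set no target or test for the CR rate, so there is none to reproduce. The one design calculation is for 12-month progression-free survival in Section 14.0. The historical median of 12 months implies a null rate of 0.50. With exact binomial tails and n = 37:

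- P(X ≥ 24 | 0.50) = 0.0494
- P(X ≥ 24 | 0.70) = 0.807

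This agrees with the stated error of 0.05 (read as one-sided) and power of 0.8. CR status does not enter the rule. Progression is measured as an increase over baseline, so losing a clearance is not by itself progression.

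**2. Four skin courses through the table.** The improvement shown is the decrease from baseline.

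| At assessment | 4 weeks later | Table as written | With the 4-week rule on CCR | Change in CR | Change in CR + PR |
|---|---|---|---|---|---|
| 100% | 100% | CCR | CCR | 0 | 0 |
| 100% | at least 50% throughout, not clear | CCR | PR | -1 | 0 |
| 100% | below 50% | CCR | neither CCR nor PR | -1 | -1 |
| 50-99% | below 50% | not PR | not PR | 0 | 0 |

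Rows three and four show the asymmetry: both patients lose the improvement within 4 weeks, and only the one who briefly cleared is credited. At the assessment itself, the fourth patient is not SD either, because that row covers decreases under 50%. Row two shows why CR + PR is less sensitive than CR.

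**3. Size.** Section 14.0 does not state a denominator for the response rates; all 37 patients are assumed here. One reclassified patient moves CR by 1/37 = 2.7 percentage points, two by 2/37 = 5.4, three by 3/37 = 8.1 and four by 4/37 = 10.8.

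The number reclassified is (patients with CCR) × (share losing clearance within 4 weeks). The documents give no value for the second factor. For the first, they offer two distant figures from other settings:

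- Section 3.0, Doxil alone, CR or unconfirmed CR in 15 of 34: 37 × 15/34 = 16.3 patients.
- Section 5.0, Targretin at an initial 300 mg/m²/day, complete clinical response in 1 of 62: 37 × 1/62 = 0.6 patients.

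The product cannot be fixed from these.

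**4. Biopsy timing side by side.**

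| Reading of *completion of treatment* | Sections 12.5 and 12.6 | Against Section 10.2 and Appendix 3 |
|---|---|---|
| End of all therapy | No such date before relapse for a responder who stays on Targretin | Conflict |
| End of Doxil, or of the 16 weeks of Targretin | Feasible, 4 weeks later | Still a different time; Appendix 3 shows no separate visit for it |

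No reading of the term brings the four statements into agreement.

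**The case against.** **CCR is only a clinical label.** Section 10.2 asks for a biopsy to document a pathological CR, Appendix 3 flags one at both tumor assessments, and Section 3.0 separates confirmed from unconfirmed CR. A reader might infer from the table that every one-visit clearance is an endpoint CR, so that CR is misclassified. The documents do not say that. They leave endpoint CR undefined, which makes misclassification a risk. The gap remains, because the table has no biopsy criterion and a biopsy at one visit does not show duration.

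**The later assessment may supply the check.** Section 12.1 uses *completion* for the end of Doxil. On that reading, or at the end of the 16 weeks of Targretin, Section 12.5 gives a response assessment 4 weeks later. A reader might infer instead that the biopsy always falls after the response is lost. That holds only if completion means the end of all therapy. Continuation is optional, and Section 10.2 and Appendix 3 still provide a biopsy. The objection stands against the stronger reading but does not remove the conflict.

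**The combined rate is hardly touched.** This is right for patients who keep at least a 50% improvement. A general upward bias in CR + PR is not shown.

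**The precedent cuts both ways.** The earlier Targretin studies confirmed responses over time but did not require a biopsy for complete response; this protocol adds one. That is fair. Biopsy and duration answer different questions, however, and the protocol already asks for duration in PR.

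**Conclusion.** The point holds as a definitional gap in a secondary endpoint. As written, a clearance seen once can count as a complete response while a lesser improvement of the same duration cannot count as partial, so the CR rate can be biased upward and can differ by site. The effect is 2.7 percentage points of CR per reclassified patient, with 37 as the denominator. CR + PR moves only for patients who fall below 50% improvement within 4 weeks. The primary endpoint, its rule of 24 of 37 and the sample size do not change.

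A total effect is tempting to quote. Taking 16.3 clearances and assuming that 10-30% are lost within 4 weeks gives 1.6 to 4.9 patients, or 4.4 to 13.2 points. The documents do not support this as an estimate: the loss range is assumed, and 15/34 comes from Doxil alone and includes unconfirmed responses. From 1/62, the same loss range gives 0.06 to 0.18 patients (0.6 × 0.1 to 0.6 × 0.3). The number affected is unknown.

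The conflict in biopsy timing is real on any reading of *completion of treatment*. What it does to a particular patient's biopsy depends on which reading a site adopts.

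**What to change.** 1. Apply the PR row's 4-week maintenance requirement to the CCR row for the endpoint.
2. State in Sections 2.0 and 14.0 whether endpoint CR is clinical or biopsy-documented, and report both rates separately.
3. Define *completion of treatment* for patients who stop at 16 weeks of Targretin and for those who continue.
4. Reconcile Sections 1.0, 12.5 and 12.6 with Section 10.2 and Appendix 3. Which biopsy time is right is for the investigators; this review does not propose one.

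**Cost.** Mostly wording, and no added biopsy. Appendix 3 places response evaluation only at weeks 14-16 and 30-32, so confirmation needs a skin score by a trained physician at an existing Targretin visit after the first assessment. Targretin starts within 2 weeks of that assessment, so its week-4 visit falls 4 to 6 weeks after it (0 + 4 to 2 + 4). After week 32, follow-up is guaranteed only every 3 months, so a 4-week check there must be scheduled. The PR rule already implies both checks; the change extends them to cleared patients. The reported CR rate may be slightly lower.

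### A patient with no tumor at baseline who develops new cutaneous tumors can be scored as a partial response and not as progression

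*Combined protocol and SAP*

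**What the plan says.** Section 12.7 gives the table binding force: "Responses will be determined by the criteria described in the table below". Its rows are:

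- PR: "Greater than or equal to 50% decrease in skin scores compared to baseline and improvement is maintained for 4 weeks".
- Stable disease: "Less than 50% decrease in skin scores compared to baseline".
- Progression in skin: a 25% or greater "increase in skin scores compared to baseline while the patient is actively taking the study drug".
- Progression in nodes: a 50% or greater "increase in the sum of the products of the greatest diameters of pathologically positive lymph nodes".

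No row mentions new lesions or new tumors. The score is a net sum: "The skin score total is derived from summing the skin score subtotals for patches, plaques and tumors or ulcers", with weights 1, 2 and 4. The same section defines a tumor by elevation: "A plaque elevated ≥5 mm is a tumor".

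Section 5.0 describes the earlier Targretin studies, in which PR required at least 50% improvement in the index lesions "without worsening, or development of new cutaneous tumors or non-cutaneous manifestations".

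Section 14.0 makes progression-free survival at 12 months the primary endpoint, with success at 24 or more of 37 patients. It defines no progression event and does not refer to the table. Sections 10.6 and 13.0 mention tumor progression and progressive disease without defining either.

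**The concern.** Eligibility (Section 6.1) starts at stage IB and does not require tumors at entry; the same section calls T3 tumor stage. A patient who enters with patches or plaques only, improves in area and then grows tumors for the first time has moved to a more serious type of skin lesion. The table can call that a response, because one total stands for both the improvement and the worsening.

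The CR + PR rate, a secondary endpoint, is directly exposed. The 12-month progression-free count is exposed if progression is read from the same table, which is a natural reading because no other definition is given. Neither the composite index-lesion assessment nor the nodal trigger closes the gap: the former is a secondary goal that follows up to four chosen lesions, and the latter does not concern skin.

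**Working it through.** **The plan's own figure.** Inputs from Section 14.0: n = 37, success at 24 or more, target rate 0.70. The null rate of 0.50 is inferred from the stated 12-month median. Exact binomial: P(X ≥ 24 | 37, 0.50) = 0.0494 and P(X ≥ 24 | 37, 0.70) = 0.807. These agree with the stated 0.05 (one-sided) and 0.80, so the sample-size arithmetic is sound.

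**The score.** With patch, plaque and tumor/ulceration areas P, Q and T in percent of body surface (Section 12.7), S = P + 2Q + 4T. Let B be the baseline score with no tumor, and suppose everything present at baseline clears while new tumors cover t%.

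- PR holds while 4t ≤ 0.5B, so t ≤ B/8.
- Skin progression is reached when 4t ≥ 1.25B, so t ≥ 0.3125B.

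| Baseline score B | Largest t still PR | Smallest t that is progression |
|---|---|---|
| 10 | 1.25% | 3.125% |
| 40 | 5% | 12.5% |
| 60 | 7.5% | 18.75% |
| 100 | 12.5% | 31.25% |

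For B = 40 (40% patch only): 4 × 5 = 20, a 50% fall; 4 × 12.5 = 50, a 25% rise. Section 12.7 equates palm plus four fingers with 1%, so 5% is about five such areas.

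**Complete clearing is not needed.**

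- 40% patch (score 40) becomes 8% patch + 3% new tumor: 8 + 12 = 20, a 50% fall. This is PR if maintained for 4 weeks.
- 20% patch + 20% plaque (20 + 40 = 60) becomes 10% patch + 5% plaque + 2% new tumor: 10 + 10 + 8 = 28. The change is 28/60 − 1 = −53.3%. This is also PR if maintained.
- The same baseline of 60 becomes 18.5% tumor only: 4 × 18.5 = 74, a rise of 23.3%. This is not progression.

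**What it could do to the primary test.** The documents give no frequency of such patients, so these figures rest on assumptions.

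- If one true failure is counted as a success, 23 true successes meet the rule: P(X ≥ 23 | 37, 0.50) = 0.094 instead of 0.049.
- If misclassification raises the apparent null rate by 2, 5 or 10 percentage points, P(X ≥ 24) is 0.080 (rate 0.52), 0.149 (0.55) or 0.335 (0.60).

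**The case against.** The strongest reply is that SWAT covers the whole skin and already counts every new tumor at weight 4. The Targretin studies followed up to five index lesions, which cannot show new ones, so they needed a separate clause. Relying on a severity-weighted total is a recognizable choice, and Section 1.0 says SWAT is used in two other protocols. This stands as far as it goes: tumors are not ignored, and extensive ones do reach the progression cut-off, at smaller areas when the baseline score is low. But a weight of 4 limits the offset without preventing it, as the table of limits shows. Nor would adding a clause make SWAT response rates directly comparable with index-lesion rates, and Section 14.0 plans no such comparison.

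The second reply concerns the primary endpoint. A reader might infer that these patients will be counted among the 24 successes and that the type I error is therefore inflated in the regimen's favor. The documents do not support that as fact:

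- Section 14.0 does not say the count is read from this table.
- Sections 10.6 and 13.0 leave room for an investigator to call progression clinically.
- The event definition behind the historical 12-month figure is not given, so the direction of bias against that benchmark is unknown.
- No frequency is available, and a patient would have to stay below the progression cut-off through month 12.

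What remains is that the table does not require new tumors to be called progression, and different centers could decide differently.

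A third reply is practical. The third SWAT column combines tumor with ulceration and fissuring, and the form records area by region, not individual lesions. It therefore cannot reliably identify a new tumor in a patient who already has some. Also, Section 13.0 removes patients with progressive disease, so a new trigger written into the progression row would act as a removal rule. Both points stand and shape the fix.

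**Conclusion.** The concern holds as a gap in the response definition. By the stated rule, a patient with no tumor at baseline can develop new cutaneous tumors over as much as one eighth of the baseline score, read as percent of body surface, and still be scored PR; progression is not reached below 0.3125 times that score. These limits follow from the plan's own weights and cut-offs and assume that all baseline disease has cleared; with residual disease the margin is smaller, as the worked examples show.

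The effect on the CR + PR rate is direct but of unknown frequency. The effect on the 24-of-37 count depends on how progression is determined, which Section 14.0 leaves open. The values from 0.080 to 0.335 are illustrations under stated assumptions, not estimates. N = 37 and the threshold of 24 need no change. The definition should be corrected because the change is small and the plan gives no reason for dropping a safeguard that it reports from the Targretin studies.

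**What to change.** Make the change as an endpoint definition for analysis:

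- For patients with no cutaneous tumor at baseline, do not count as PR any patient with a confirmed new tumor, and count that tumor as a progression event in the 12-month progression-free count. Use the elevation threshold of 5 mm or more and the 1-4 week confirmation already in Section 12.7. State whether a PR established before the tumor appeared is kept.
- In the third SWAT column, mark tumor separately from ulceration or fissuring.
- State in Section 14.0 that progression-free survival events use this definition.

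This should not be written as a new rule for removing patients from treatment. The sponsor should reconcile the endpoint definition with the undefined progression wording in Sections 10.6 and 13.0. Patients with tumors at baseline stay under the existing score rules, because the form does not track individual lesions.

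The cost is one extra mark on the SWAT form and possibly a slightly lower response rate and progression-free count. No scheduled visit or test is added, although an unscheduled confirming look may be needed where a new tumor would not prompt one under the present rule.
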